Comparison of the Efficacy of Single and Double Puncture Arthrocentesis in Treatment of Temporomandibular Joint Disc Displacement Without Reduction

Date: 20/03/2020

This document contains study design and statistical analysis plan of the study entitled "Comparison of the Efficacy of Single and Double Puncture Arthrocentesis in Treatment of Temporomandibular Joint Disc Displacement Without Reduction".

Study Design:

This is a two-armed, randomized, parallel interventional clinical study enrolling 36 patients with temporomandibular joint disc displacement without reduction (DDwoR).

*Eligibility:**Inclusion Criteria:*

- Clinical diagnosis of Temporomandibular joint (TMJ) disc displacement without reduction.
- Restricted mouth opening

Exclusion criteria:

- History of systemic disease effecting TMJ.
- History of previous TMJ surgery

Patients were grouped according to the treatment they received: Single Puncture Arthrocentesis as group SPA, Double Puncture Arthrocentesis as DPA.

Double puncture arthrocentesis technique:

Posterior puncture method was used as described by Alkan and Etoz for DPA. A straight line was drawn with a marker pen along the skin from the middle portion of the auricular tragus to the lateral chantus. The first puncture point was marked 10 mm anterior and 2 mm inferior to the tragus and the second 7 mm anterior and 2 mm inferior to the tragus. After local anesthesia, upper joint cavity was irrigated with 200 mL of Lactated Ringer's (RL) solution by inserting two 21- gauge needle. At the end of the procedure, after withdrawn of one of the needles, 1 mL of sodium hyaluronate (SH) was injected into the upper TMJ compartment through the other needle.

Single Puncture Arthrocentesis Technique:

SPA was performed with one needle (SPA Type-1 according to Senturk and Cambazoglu). The first reference point in DPA was used as the needle entry point fort he SPA. With this technique, the inflow and outflow of solution were provided through the same cannula and lumen of one 21-gauge needle as described by Guarda-Nardini et al. The joint was irrigated with 200 mL of RL solution under high pressure. At the end of the procedure 1 mL of SH was injected through

the needle

Outcome measures:

1. The Rate of Pain on Function (PoF) assessed by Numerical pain Scale (NRS)

Patients rated their pain on function (pain during chewing or speaking etc.) on a Numeric Rating Scale (NRS) (0–10 where 0 is no pain and 10 is the worst pain imaginable).

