Patients were evaluated at preoperatively and postoperatively 1st week, 1st month, 3rd month, 6th month.

2. The measurement of pain-free maximum mouth opening (MMO) in millimeters:

Pain-free MMO was measured as the distance between the incisal edges of the upper and lower incisors by a caliper while patient's mouth is open as possible without any assistance and without pain in masseter muscle. Three measurements were performed, and their average is recorded. Patients were evaluated at preoperatively and postoperatively 1st week, 1st month, 3rd month, 6th month.

3. The rate of pain at rest (PaR) assessed by Numerical pain Scale (NRS)

Patients rated their pain level at rest on a Numerical pain Scale (NRS)(0–10 where 0 is no pain and 10 is the worst pain imaginable). Patients were evaluated at preoperatively and postoperatively 1st week, 1st month, 3rd month, 6th month.

4. Measurement of Duration of the Procedure in Minutes.

Total time for arthrocentesis was noted at the end of the procedure.

Patients were evaluated at the end of the procedure

5. Measurement of the easiness of the procedure to the operator by using Visual Analog Scale (VAS):

The operator rated the degree of easiness of the procedure on a VAS as 0-very easy 10-very difficult to perform at the end of the procedure

6. The rate of treatment tolerability assessed by 5-point Likert-type scale:

The degree to which overt adverse effects and post operative complications (pain, feeling of pressure in TMJ area and disturbing sound) can be tolerated by the patient. Patients were asked to rate the tolerability on a 5 point scale as 0- lowest, 4-highest at operation day, 1st week, end of follow up period (6th month)

7. The rate of chewing efficiency by using Visual Analog Scale (VAS):

Patients rated the chewing efficiency on a VAS as 0-can only eat semi-liquid foods, 10-eat any solid-food. Patients were evaluated at preoperatively and postoperatively 1st week, 1st month, 3rd month, 6th month.

8. Rate of perceived effectiveness of the treatment by using 5-point Likert-type scale:

Patients rated the subjective treatment effectiveness on a 5-point scale as 0- lowest, 4 highest values at the end of the follow up period (6th month).

9. Measurement of Lateral Movement of the mandible towards the affected Temporomandibular joint (TMJ) in millimeters

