Lateral Movement of the mandible towards the affected Temporomandibular joint (LT) was measured as the distance between the midlines of the upper and lower incisors by a caliper while patient's mandible was shifted towards the affected TMJ. Three measurements were performed, and their average is recorded. Patients were evaluated at preoperatively and postoperatively 1st week, 1st month, 3rd month, 6th month.

10. Measurement of Lateral Movement of the mandible away from the affected Temporomandibular joint (TMJ) in millimeters

Lateral Movement of the mandible away from the affected Temporomandibular joint (LA) was measured as the distance between the midlines of the upper and lower incisors by a caliper while patient's mandible was shifted away from the affected TMJ. Three measurements were performed, and their average is recorded. Patients were evaluated at preoperatively and postoperatively 1st week, 1st month, 3rd month, 6th month.

11. Measurement of protrusive movement of the mandible in millimeters:

Protrusive movement of the mandible was measured as the distance in horizontal direction between the incisal edges of upper and lower incisors by a caliper when mandible moves forward. Patients were evaluated at preoperatively and postoperatively 1st week, 1st month, 3rd month, 6th month.

Statistical Analysis:

IBM SPSS 22 was used to analyze the data (IBM SPSS Statistics for Windows, Version 22.0. Armonk, NY: IBM Corp.). Descriptive statistics of the variables were presented as mean \pm standard deviation in statistical analysis. Normality of distribution for continuous variables was evaluated using the Kolmogorov-Smirnov test. Depending on whether the statistical hypotheses were fulfilled, either the Student's t-test or the Mann-Whitney U test was used to compare the independent continuous variables between the two groups, Wilcoxon signed rank test was used for intra-group evaluation of variables according to baseline such as PoF ve MMO. Statistical significance level was accepted as $p < 0.05$.

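### No between-arm test is fixed for any outcome: a loosely specified Kolmogorov-Smirnov pre-test on the trial data chooses between Student's t-test and Mann-Whitney

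*Combined protocol and SAP*

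**What the plan says.** The Study Design section describes a "two-armed, randomized, parallel interventional clinical study enrolling 36 patients". It gives no allocation ratio.

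The Statistical Analysis section states: "Normality of distribution for continuous variables was evaluated using the Kolmogorov-Smirnov test". The between-arm rule follows: "Depending on whether the statistical hypotheses were fulfilled, either the Student's t-test or the Mann-Whitney U test was used". The section does not give:

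- the version of the K-S test, or its significance level;
- whether it is run in each arm or on pooled data;
- whether the choice is made once per outcome or again at each visit;
- whether the assumptions in question go beyond normality.

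By contrast, the within-arm method is fixed: "Wilcoxon signed rank test was used for intra-group evaluation of variables according to baseline". Descriptive statistics are always mean and SD, whichever test is chosen.

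Both the pre-test and the between-arm rule are worded for continuous variables. Items 6 and 8 under Outcome measures are five-category ratings (for item 8, "Patients rated the subjective treatment effectiveness on a 5-point scale"). No other between-arm method is named for them.

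**The concern.** A reader of the plan cannot tell which test will produce any between-arm p-value until the data have been seen, and even then the answer depends on an unstated version of the pre-test. The t-test compares means and Mann-Whitney compares ranks. If the choice changes between week 1 and month 6, the results for one outcome no longer describe one quantity over time. If the pre-test almost never rejects, the t-test is kept for skewed data, where it loses power. Two analysts following the same text could reach different verdicts on a borderline result.

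**Working it through.** The plan contains no figure to reproduce on this point: 36 patients is stated without an effect size, SD or power.

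**Inputs.** From the documents: 36 patients, two arms, significance level 0.05, four post-operative visits, and 0-10 pain scales. Assumed: 36/2 = 18 per arm; pre-test at 5% in each arm; Mann-Whitney if either arm rejects; two-sided tests; all distributions.

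**1. Comparisons affected.** Seven outcomes (PoF, PaR, MMO, chewing, LT, LA, protrusion) × 4 post-operative visits = 28. Adding duration and easiness gives 30. The two 0-4 scales add 3 + 1 = 4, for a total of 34.

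**2. Size of the pre-test.** The K-S statistic D is the largest gap between the empirical distribution and a normal curve with mean and SD estimated from the same 18 values. The 5% critical value is 0.309 from the plain table and 0.202 with the Lilliefors correction (simulated). On normal data the plain test rejects about 0.007% of the time and Lilliefors 5.1%.

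**3. Rejection and mixing.** If one arm rejects with probability q, Mann-Whitney is chosen with probability r = 1 − (1 − q)². With independent visits, the chance that four visits do not all get the same test is 1 − Πr − Π(1 − r). For one distribution held at all four visits:

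| Assumed distribution | One arm rejected: Lilliefors / plain | Mixed tests: Lilliefors / plain |
|---|---|---|
| Normal | 5.1% / about 0% | 33% / 0.1% |
| Integer NRS, latent mean 5, SD 2 | 26% / 0.3% | 87% / 3% |
| Integer NRS, latent mean 2, SD 2 | 44% / 0.8% | 78% / 7% |
| Lognormal, sigma 0.5 | 31% / 1% | 87% / 8% |
| Exponential | 53% / 3% | 64% / 21% |
| Integer NRS, latent mean 0.5, SD 2 | 96% / 40% | 0.5% / 81% |

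Check of the first row: r = 1 − 0.949² = 0.099, and 1 − 0.099⁴ − 0.901⁴ = 0.34, against 33% from the simulated r. With correlated visits (0 to 0.8) it is 32-34%.

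**4. Pain falling over the visits.** Take latent means 4, 3, 2 and 1.5, SD 2.2, between-visit correlation 0.5, rounded and clipped to 0-10. Lilliefors rejects one arm in about 22%, 25%, 43% and 64% of cases. Then r = 0.392, 0.438, 0.675, 0.870; Πr = 0.101; Π(1 − r) = 0.014; and mixing = 1 − 0.101 − 0.014 = 0.885. Simulation with the correlation gives 87-88%, against 12% for plain K-S. The two versions choose different tests at 39-78% of visits.

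**5. Does the choice matter?** With a true latent shift of 1.5 points, the p < 0.05 verdict differs between the two versions at one or more of the four visits in 12-13% of trials. Per visit this is 2.6-4.4%, and about 1% for unrounded data. The t-test and Mann-Whitney disagree on significance in 6% of normal trials (shift 0.95 SD) and 14% of lognormal trials (sigma 0.5, shift 0.5). In that lognormal case power is 69% for the t-test and 81% for Mann-Whitney. For more skewed data (lognormal, sigma 0.8 to 1.0) the gap is smaller: 46-47% with the plain pre-test, 49-51% for Mann-Whitney and 52-53% for a t-test on logs.

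**6. Type I error.** The two-stage rule gives 4.7-5.7% across the scenarios. A single fixed test gives 4.7-5.4%.

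**7. What a fixed, baseline-adjusted method gains.** Adjustment divides the residual SD by 1/√(1 − ρ²). For an effect of 0.8 SD and correlation ρ = 0.5, the standardised effect becomes 0.8/√0.75 = 0.92. The noncentrality with 18 per arm rises from 0.8 × √(18/2) = 2.4 to 2.77, and power from about 65% to about 76%.

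**The case against.** The strongest reply is that error control is intact, so little is at stake. That stands: type I error stays near 5%, and a conclusion that the procedure inflates false positives would be wrong. A single trial also uses only one version of the pre-test, so disagreement between versions is a reproducibility problem, not an error rate.

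Several stronger readings are tempting and are not supported:

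- *The test is chosen separately at each visit.* The text does not say so. It leaves the unit of decision open, and one choice per outcome would remove mixing over visits.
- *The pre-test is not a valid 5% test.* This is true of plain K-S. It is false of Lilliefors on continuous normal data (5.1%).
- *A faulty pre-test therefore produces mixed methods.* The two faults mostly belong to different versions. Where plain K-S hardly ever rejects, the t-test is nearly always kept and mixing is rare. Lilliefors mixes tests even where its size is correct.
- *Lilliefors rejects most integer pain data.* With the falling means above, it rejects more than half of single arms at only one of four visits.
- *The 0-4 ratings are sent through the pre-test.* The rule is worded for continuous variables. The supportable point is that these items have no clear between-arm test.

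It is also fair to say that baseline adjustment goes further than removing the pre-test requires. It is included because the pre-operative values are already collected and the gain in power is larger than anything the choice of K-S version would recover in the most skewed case above.

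**Conclusion.** The point holds as a gap in pre-specification. The plan fixes no between-arm test for any outcome, and leaves open the version, unit and level of the pre-test that chooses one. If Lilliefors is applied per visit, mixing over four post-operative visits is about 87% for a falling pain score and about a third for normally distributed millimetre outcomes. With plain K-S the corresponding range is 0-12%.

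These figures rest on 18 per arm, the either-arm rule and invented distributions, because the documents give no means, SDs or shapes. They can move a long way: if most patients score near zero, the pattern reverses (0.5% with Lilliefors, 81% with plain K-S). The harm is to interpretability, reproducibility and some power. The plan should be changed, but its error rate is not in question.

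**What to change.** Delete the K-S step and name one between-arm method per outcome, the same at every visit:

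- **PoF, PaR, chewing VAS, MMO, LT, LA, protrusion:** a linear model with arm and the pre-operative value, reporting the adjusted mean difference and its confidence interval. Add a rank-based analysis, labelled as sensitivity.
- **Easiness VAS and the two 0-4 scales:** Mann-Whitney with a matching rank-based effect measure. These have no pre-operative value to adjust for.
- **Duration:** one test named now, either Mann-Whitney or a t-test on log minutes (reported as a ratio).

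The cost is a few sentences in the Statistical Analysis section and no new data. A mean-based model is slightly less efficient if an outcome is very skewed, which the rank-based sensitivity analysis covers. Because the section is written in the past tense, the change should be dated and its timing relative to any look at the data stated.

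### The between-arm t-test pools the variances and arm sizes are not fixed; Welch's t-test would be a small, nearly free safeguard, chiefly for procedure duration and operator ease

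*Combined protocol and SAP*

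**What the plan says.** The Statistical Analysis section offers two between-arm tests: "either the Student's t-test or the Mann-Whitney U test was used to compare the independent continuous variables between the two groups". The choice is made "Depending on whether the statistical hypotheses were fulfilled", a condition that is not spelled out. The only assumption check named is for normality: "Normality of distribution for continuous variables was evaluated using the Kolmogorov-Smirnov test". No variance check and no unequal-variance test appears. The significance level is 0.05; sidedness is not stated.

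The Study Design section describes a "two-armed, randomized, parallel interventional clinical study enrolling 36 patients". It gives no allocation ratio, blocking or number per arm. The sentence that introduces the arms, "Patients were grouped according to the treatment they received", adds no arm sizes.

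The outcomes most exposed are number 4, procedure duration ("Total time for arthrocentesis was noted at the end of the procedure"), and number 5, the operator's 0–10 rating of ease. Both are recorded once, at the end of the procedure.

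**The concern.** Student's t-test estimates one common variance from both arms. That is harmless if the SDs are equal, and nearly harmless if the arms are the same size. If both conditions fail, the standard error is wrong. It is too small when the smaller arm is the more variable one, and too large in the opposite case.

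Unequal spread is plausible for duration and ease because the techniques differ mechanically. One places two needles; the other passes inflow and outflow through a single lumen under high pressure. Neither outcome has a preoperative value, so baseline adjustment cannot absorb any of the spread. At stake is whether a finding that one technique is faster or easier was really tested at 5%. The issue arises with perfectly normal data, so it is separate from any question about the Kolmogorov-Smirnov check.

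**Working it through.** **Inputs from the documents:** total N = 36; significance level 0.05; tests Student's t or Mann-Whitney.

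**Assumed, because the documents are silent:** two-sided testing; splits 18/18, 16/20 and 14/22; SD ratios 1.5, 2 and 3; normal data unless stated; simple randomisation where probabilities of a split are given.

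**Step 1. The plan's own figure.** With equal SDs at 18/18, 100,000 simulated null trials (Monte Carlo standard error 0.07 points) give 5.0% for Student and 5.1% for Mann-Whitney. The nominal 5% is reproduced.

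**Step 2. Why the split matters.** Let arm 1 have SD 1 and arm 2 have SD 2.

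- True variance of the mean difference: V = 1/n₁ + 4/n₂
- Variance that the pooled test estimates, on average: P = [(n₁−1)·1 + (n₂−1)·4]/34 × (1/n₁ + 1/n₂)

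Worked example, n₁ = 22 and n₂ = 14:

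- V = 0.0455 + 0.2857 = 0.331
- P = (21 + 52)/34 × 0.1169 = 2.147 × 0.1169 = 0.251
- V/P = 1.32, so the pooled test understates the variance.

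At 18/18, V = 5/18 and P = 2.5 × 2/18 = 5/18. The two are identical, and only the degrees of freedom are slightly off.

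**Step 3. Simulated false-positive rates at SD ratio 2.**

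| n with SD 1 / n with SD 2 | V | P | V/P | Student | Mann-Whitney |
|---|---|---|---|---|---|
| 18 / 18 | 0.278 | 0.278 | 1.00 | 5.3% | 5.9% |
| 20 / 16 | 0.300 | 0.261 | 1.15 | 6.8% | 6.6% |
| 22 / 14 | 0.331 | 0.251 | 1.32 | 9.0% | 7.5% |
| 16 / 20 | 0.263 | 0.301 | 0.87 | 3.8% | 5.0% |
| 14 / 22 | 0.253 | 0.333 | 0.76 | 2.8% | 4.0% |

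Independent runs agree to about 0.2 points. Mann-Whitney is shown without continuity correction; with it, the 18/18 figure is 5.5%. At 18/18, Student lies at about 5.2–5.5% for SD ratios 1.5 to 3. Welch lies between 4.8% and 5.2% for normal data in every split and ratio tried.

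**Step 4. How likely the inflating case is.** Under Binomial(36, 0.5):

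- A split of 16/20 or worse, in either direction, has probability 0.618. The more variable arm is the smaller one in half of these: 0.618/2 = 0.309.
- A split of 14/22 or worse has probability 0.243, and 0.243/2 = 0.121.
- Exactly 18/18 has probability 0.132.

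Averaged over all splits, so that inflated and conservative cases offset, Student's rate is about 5.5% at SD ratio 2 and 6.1% at ratio 3.

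**Step 5. Skewed data.** With gamma data (shape 4), equal means and SD ratio 2, Mann-Whitney rejects in 8.5% of null trials at 18/18 and 10.0% at 14/22 with the smaller arm more variable. Over all skewed settings tried, Welch ranges from 4.7% to 6.2%.

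**Step 6. Price of Welch when SDs are equal.** For an assumed true difference of 0.95 SD, power goes from 78.9% to 78.8% at 18/18 and from 77.2% to 76.7% at 14/22.

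**The case against.** The strongest reply is that 9.0% requires several things at once: an SD ratio near 2, unblocked randomisation, a clearly uneven split, and the larger SD in the smaller arm. The documents state none of them. Both techniques use the same 200 mL irrigation and the same 1 mL injection, so a twofold difference in spread is conjecture. Silence on the allocation ratio is a reporting gap, and it is not evidence of 14/22. Duration and ease are also items 4 and 5 of 11 outcomes, behind pain on function and mouth opening. All of this stands, and it limits the point to a refinement.

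Three stronger readings are tempting and should be resisted.

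- A reader might infer that neither test holds 5% whenever SDs differ. At 18/18 Student's t very nearly does.
- A reader might set the 62% and 24% chances of an uneven split beside the inflated rates. Those chances cover both directions; in half of the cases Student is conservative.
- A reader might infer that the plan uses Mann-Whitney to deal with unequal variances. The text does not say so. Its switching condition is vague, and normality is the only check it names.

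Mann-Whitney also deserves a fair statement: it keeps its level when the two distributions are identical. It drifts only when read as a test of equal means or medians. That reading is likely here, because the plan summarises variables as mean and SD.

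**Conclusion.** The point holds as a small, inexpensive improvement. The plan names a pooled-variance test, names no unequal-variance alternative, and does not fix the equal arms that would largely protect that test. The possible error runs in either direction. At SD ratio 2 it spans 2.8% to 9.0% across splits no worse than 14/22, but the average under simple randomisation is only about half a point above nominal. These sizes rest on assumed SDs, an assumed allocation method and normal data. The documents neither supply nor exclude these conditions, so they do not show that any comparison in this trial is actually mis-sized.

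**What to change.** In the Statistical Analysis section, replace Student's t-test with Welch's unequal-variance t-test wherever two means are compared, duration and operator ease in particular. Apply it by default, without a preliminary variance test: a Levene-then-choose rule still gave 5.5% at 16/20 and 6.1% at 14/22 (SD ratio 2, smaller arm more variable). Do not rely on Mann-Whitney as a remedy for unequal variances. Stating the allocation ratio and the number per arm would let a reader judge how much this matters.

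The cost is a wording change and less than 1 point of power when SDs are equal. No extra data are needed. One limit remains: Welch is only approximate for skewed data (up to about 6% in the settings tried), which is relevant to a duration and to a bounded 0–10 rating.

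### Seven outcomes are measured at baseline and four later visits, but the only arm comparison is a two-sample test with no baseline covariate, longitudinal model or named main time point

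*Combined protocol and SAP*

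**What the plan says.** The Study Design section describes a "two-armed, randomized, parallel interventional clinical study enrolling 36 patients". Under Outcome measures, items 1–3, 7 and 9–11 (pain on function, mouth opening, pain at rest, chewing efficiency, the two lateral movements and protrusion) share one schedule: "Patients were evaluated at preoperatively and postoperatively 1st week, 1st month, 3rd month, 6th month". Each patient therefore contributes a baseline and up to four follow-up values on each of seven outcomes.

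For the arm comparison, the Statistical Analysis section offers Student's t-test or, as its alternative, "the Mann-Whitney U test was used to compare the independent continuous variables between the two groups", with the choice depending on a check of assumptions. Baseline enters in one place only: "Wilcoxon signed rank test was used for intra-group evaluation of variables according to baseline such as PoF ve MMO". That is a comparison within each arm.

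The section does not say at which visit the arms are compared, whether raw values or changes are compared, which visit counts most, or how several p-values are to be read together. It also gives no SD, effect size, power or between-visit correlation, and no rule for missed visits.

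**The concern.** A two-sample test takes one number per patient, and the plan defines no summary over visits. The natural reading is therefore one test per visit: four for each repeated outcome and 7 × 4 = 28 in all. Three things follow on that reading.

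- The preoperative value, already collected, does nothing to sharpen the arm comparison.
- One outcome can be significant at one visit and not at the next, with no rule for which result answers the efficacy question.
- Four unadjusted looks at each outcome raise the chance of a false positive above the nominal 5%.

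In a trial of 36 patients, both the unused information and the lack of a single answer matter.

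**Working it through.** **Inputs.** From the documents: 36 patients, significance level 0.05, and four post-operative visits plus baseline. Assumed, because they are not stated: 18 per arm, a two-sided test, no missed visits, an arm effect of 0.6 SD, and equal correlation ρ between visits. The plan gives no power figure to reproduce.

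**Formula.** With the single-visit variance set to 1, power comes from the noncentral t distribution with noncentrality d/√V × √(18/2) = 3d/√V. For d = 0.6 this is 1.8/√V. Degrees of freedom are 34, or 33 with a baseline covariate. The variance factor V is:

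- one visit: 1
- one visit, baseline-adjusted: 1 − ρ²
- four-visit average: (1 + 3ρ)/4
- four-visit average, baseline-adjusted: (1 + 3ρ)/4 − ρ²

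| Analysis | V, ρ = 0.4 | Power | V, ρ = 0.6 | Power |
|---|---|---|---|---|
| One visit | 1 | 42% | 1 | 42% |
| One visit + baseline | 0.84 | 48% | 0.64 | 59% |
| Average of four | 0.55 | 65% | 0.70 | 55% |
| Average + baseline | 0.39 | 80% | 0.34 | 85% |

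These treat the baseline slope as known. Estimating it costs a point or so.

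**Higher correlation.** Averaging alone gives 47.5% at ρ = 0.8 and 44% at ρ = 0.9.

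**Weak baseline.** Let baseline correlate only 0.2 with each later visit.

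- Post-operative correlation 0.6: V = 0.70 − 0.04 = 0.66, power 58%.
- Post-operative correlation 0.8: V = 0.85 − 0.04 = 0.81, power 49%.

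**Effect that builds up.** With 0, 0.2, 0.4 and 0.6 SD over the four visits, the average effect is 0.3 SD. The baseline-adjusted average has noncentrality 0.9/√0.39 = 1.44 to 0.9/√0.34 = 1.54, so power is 29–32%. A plain month-6 test, facing 0.6 SD, keeps 42%. With 0.6 SD at month 6 only, the average effect is 0.15 SD and power is about 11–12%.

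**If changes from baseline were meant.** The variance of a change is 2(1 − ρ): 1.2 at ρ = 0.4 and 0.8 at ρ = 0.6. Baseline adjustment gives 0.84 and 0.64, so it is more precise in both cases.

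**Four separate t-tests per outcome** (simulation, 40,000 trials per row):

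| ρ | At least one p<0.05, no effect | Some but not all visits significant, constant 0.6 SD |
|---|---|---|
| 0.4 | 17% | 65% |
| 0.5 | 15% | 60% |
| 0.6 | 15% | 53% |
| 0.7 | 13% | 45% |
| 0.8 | 12% | 38% |
| 0.9 | 9% | 27% |

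If the four tests were independent, the first rate would be 1 − 0.95⁴ = 18.5%. With a constant 0.6 SD effect, at least one visit is significant in 69–76% of trials at ρ = 0.4–0.6.

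**The case against.** The strongest reply is that no fixed power loss can be laid at the plan's door. A reader might infer that about half the available power is wasted, by setting 42% against 80–85%. That contrast combines two separate changes, averaging over visits and adjusting for baseline. It also needs a constant effect and a baseline as predictive as a neighbouring follow-up visit. An intervention lies between baseline and follow-up, and entry requires restricted mouth opening, so the baseline correlation may be low. Averaging alone closes far less of the gap: the single-visit test loses about 36% of the power at ρ = 0.4 (42% against 65%) and 6% at ρ = 0.9 (42% against 44%). With complete data, a mixed model adds essentially nothing at a single visit beyond what the baseline covariate gives. This part of the reply stands.

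Other tempting readings also go beyond the text. The plan does not say that each visit is tested separately, and it designates no month-6 test. It does not say that patients who miss a visit are dropped. Conflicting verdicts are possible, not certain, and become less common as correlation rises.

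It can also be said that testing every visit does not lack power to find something. That is so, at 69–76% for any visit, but the gain is bought with an uncontrolled error rate, which supports the concern.

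Finally, the plan has a rank test for non-normal data, and a linear mixed model on bounded 0–10 scales does not. A sensitivity analysis should cover this.

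**Conclusion.** The point holds as a gap in the analysis plan. For seven repeatedly measured outcomes there is no named contrast, no baseline adjustment in the arm comparison and no model linking the visits.

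On the natural reading, the firmest consequence is the 15–17% chance per outcome of a spurious significant visit at correlation 0.4–0.6, falling to about 9% at 0.9. The lack of a rule for reading discordant visits goes with it.

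The precision gain is real in direction but unknown in size. It ranges from a few points to a near doubling of power under a constant 0.6 SD effect, and the averaged contrast does worse than a month-6 test if the effect arrives late. All these figures assume 18 per arm, equal correlation between post-operative visits and complete data. The change is worth making because it is cheap, but it should not be justified by a single power figure.

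**What to change.** For each of the seven repeated outcomes, specify one mixed model for repeated measures fitted to the four post-operative visits. Include arm, visit, arm-by-visit and the preoperative value, with within-patient correlation and small-sample degrees of freedom.

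- Name one contrast in advance as the main one, either month 6 or the four-visit average. Choose it according to when a difference between the techniques is expected.
- Report both contrasts with 95% confidence intervals, and treat the other visit-by-visit results as descriptive.
- For the bounded 0–10 scales, keep a rank-based or baseline-adjusted sensitivity analysis.
- If visit-by-visit testing was not the intention, state what was.

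The cost is SAP wording and modest analysis work on data already scheduled for collection. A patient who misses a visit still contributes the visits attended. The downsides are that a covariance structure must be chosen and that an averaged contrast dilutes an effect confined to one visit, which is why both contrasts are shown. Naming a contrast settles multiplicity across visits within an outcome. It does not settle multiplicity across the seven outcomes, which needs a named primary outcome.
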